2.1.3 Time window, baseline and post-baseline definitions, and missing data handling

Screening phase (Hour -16): The screening phase is the time period prior to randomization, which should be within 16 hours after presentation. After obtaining written informed consent, the subject will be evaluated for eligibility to participate in to the study.

All references to index hospitalization refer to the initial hospitalization for acute heart failure (AHF).

Baseline (Hour 0/Day 1): The assessments identified in the eCRF as baseline assessments will be used as the baseline reference for all analyses. The baseline date and time will be considered the date and time of initiation of study drug, or randomization if the subject was not treated with study drug. If the value is missing, the last value at screening visit will be used.

Post-baseline phase: The post-baseline phase begins at the time when study drug administration starts (Hour 0/Day 1) and ends with the last study assessment/last follow-up or the death of subject. For subjects who did not receive study drug, the post-baseline phase begins at time of randomization.

Time window: For the scheduled post-baseline visits, time window is not defined; the data will be used as reported in eCRFs (i.e., the actual assessment times will not be used to

[figure not shown]
reclassify the time point at which a measure was taken). The by-visit report will be presented by protocol scheduled visit. Time-to-event analyses will be based on actual date and time as reported when available.

Missing data handling

Missing data handling for efficacy endpoints are discussed in [Section 2.2](#), Efficacy evaluation. In general, missing values of other assessment/measurement will not be imputed unless otherwise specified.

The dates for efficacy endpoint events and AE events should be reported as instructed in eCRFs. If a partially missing date cannot be resolved after data query, the following is the general rule for imputation as necessary only if the calculation is needed (e.g., to calculate time-to-event):

- a) if only the month of the event is known, then the 15th day of this month will be imputed for a missing day in case the month and year are after the month and year of double blind treatment start. If the month and year are equal to the double blind treatment start then the event date will be imputed by the treatment start date.
- b) if only the year of the event is known, then the 1st July will be imputed for a missing day and month in case the 1st July is after double-blind treatment start (otherwise treatment start date will be used), or
- c) for events occurring between two visits after randomization, without other information available, the date/time in the middle of these visits will be used.

Adverse Events with incomplete start dates will be considered treatment emergent (incident) if it is not obvious from the partial date whether the event onset was after study drug was initiated.

For lab data which exceed limit of detection, e.g. data reported as >8 or >10, the threshold value 8 or 10 will be used in the summary descriptive statistics, and original reported data will be listed in the listings.

2.1.4 Subgroup definitions

The subgroups are defined based on subjects' status at screening (if screening value is not collected, Hour 0 value will be used).

Key subgroups that will be considered in subgroup analyses of the primary and key secondary endpoints are listed in [Table 2-3](#).

Table 2-3 Specification of key subgroups at screening

Variable	Source	Categories
Age group	Derived	<65, ≥65; <75, ≥75 years
Sex	eCRF	Male, Female
Preserved ejection fractions/Reduced ejection fractions (PEF/REF) (most recent value in last 12 months)	Derived	<50%, ≥50%; <40%, ≥40% (CRF: heart failure and diabetes history)
Prior history of heart failure	eCRF	Yes, No (CRF: heart failure and diabetes history)

Table 2-4 Specification of additional subgroups at screening

Variable	Source	Categories
Systolic blood pressure	Derived	<140, ≥140 mmHg
Heart rate	Derived	< 80, ≥ 80 bpm
History of Ischemic heart disease	eCRF	Yes, No (CRF: heart failure and diabetes history)
History of diabetic mellitus	eCRF	Yes, No (CRF: heart failure and diabetes history)
History of atrial fibrillation or flutter	eCRF	Yes, No (CRF: protocol solicited medical history)
Time from presentation to randomization	Derived	<2, 2-10, >10 hours
Intravenous (IV) nitrate use at randomization	eCRF	Yes, No
Lymphocytes	Local Lab, Derived	≤12, >12%
eGFR	Local Lab, Derived	<30, ≥30; <50, ≥50; <60, ≥60 mL/min/1.73 m ²

2.1.5 Subject disposition

The number of subjects randomized (RAN) and included in each analysis population (FAS, PPS, and SAF) will be presented by treatment group. The number of subjects screened, completed and discontinued from screen phase, and the reasons for screen failures will be provided. The number and percentage of subjects in the FAS who completed, discontinued the study, and the reason for discontinuation will be presented for each treatment group and overall (treatment groups combined).

The number of subjects screened and randomized per country will be presented for FAS.

For each subject, the length of follow-up (days) will be computed by subtracting the study drug initiation date (or the randomization date for subjects not treated with study drug) from the end of study date [REDACTED].

2.1.6 Background and demographic characteristics

Subject demographics (age, sex, ethnicity, race, weight, height and BMI) and baseline characteristics will be summarized for the FAS populations. Screening BNP, NT pro-BNP and estimated eGFR, laboratory values as reported by the investigator will be summarized with standard descriptive statistics. The number and percentage of subjects who were hospitalized for heart failure in the past year and subjects on IV nitrates at the time of randomization will both be presented.

For baseline comparability, treatment groups will be compared using the chi-squared test for categorical variables and using t-test for continuous variables. The p-values will be provided for descriptive purpose and will not be considered to define any formal basis for determining factors to be included in statistical models. If an imbalance of treatment groups with respect to some variables does occur, supplemental analyses with addition of these variables in model may be performed to assess the potential impact on efficacy as appropriate.

In addition, violations of inclusion and exclusion criteria and other protocol deviations will be listed. Major protocol deviations resulting in subject exclusion from any analysis ([Table 2-1](#)) will be summarized by treatment group for RAN population.

2.1.7 Medical history

Medical history data will be summarized by treatment group for FAS.

[figure not shown]
Protocol solicited medical history

The number and percentage of subjects will be presented for each protocol solicited event as pre-printed list in eCRFs.

Heart failure and diabetes history

The number and percentage of subjects including but not limited to who had history of heart failure, New York Heart Association (NYHA) class, primary heart failure etiology (ischemic/non-ischemic), who were hospitalized for heart failure, ejection fraction (<40%, ≥40%; <50%, ≥50%), who were on heart transplant list, and who had history of diabetes mellitus will be presented for FAS. The number of HF hospitalization in the past year and ejection fraction (%) will also be presented.

Other medical history

The number and percentage of subjects with each medical condition will be provided by treatment group for the FAS.

2.1.8 Other subject history information

Drug abuse, smoking, and alcohol histories will also be summarized for the FAS by presenting the number and percentage of subjects for each pre-printed questionnaire.

2.1.9 Study medication

In general, study drug administration details will be summarized for the FAS and SAF populations. This will include time from presentation to randomization (hours), time from first IV loop diuretic for the current AHF episode to randomization (hours), time from earlier of presentation to hospital or first IV loop diuretic to randomization (hours), on IV nitrates at randomization (yes/no), time from randomization to study drug administration (hours), study drug administered on either day (yes/no), reason study drug not administered, actual study drug received, and the number of days infused (one or two).

The duration of study drug administration (in hours) and the total volume of study drug administered (estimated from the total time and rate of infusion) will be summarized. In addition, the number of subjects whose study medication dose was lowered or discontinued prematurely, and the reasons for discontinuation, including dose decreased due to blood pressure decrease (yes/no) will be summarized by treatment group.

2.1.10 Concomitant medications, surgical and medical procedures

Unless specified, the use of all concomitant medications will be summarized using the SAF population.

Major cardiovascular and non-cardiovascular classes of medication taken by a subject approximately 30 days prior to study drug initiation and on a daily basis while hospitalized through Day 5, at Discharge, and at Day 14 and other follow-up visits will be recorded. At each visit, only those medications currently being taken or those were taken within 24 hours prior to the given visit will be collected. These medications are predefined by the code lists and will be collected in each of following eCRFs:

- IV loop diuretic medications for heart failure (collected since initial presentation of HF)
- IV medications other than loop diuretics (collected since initial presentation of HF)
- Other non-IV prior medications (30 day prior to screening, within 24 hours at each visit)
- Other prior and concomitant medications

IV loop diuretic medications

IV loop diuretic medications for heart failure include Bumetanide, Etacrynic acid, Ethacrynic acid, Furosemide, Torasemide, Torsemide and Piretanide.

The number and percentage of subjects using each medication will be summarized by protocol scheduled time point. Each time point reflects medication use within the preceding 24 hours.

The total daily dose for each medication will also be presented at each time point. In addition, cumulative use (total dose as the sum from Day 1) at 48 hours (24 hours/Day 1 and 48 hours/Day 2), and at Day 5 (from 24 hours/Day 1 to Day 5) in furosemide equivalent (mg) will be summarized. The calculation of furosemide equivalents (mg) for Bumetanide, Etacrynic acid/Ethacrynic acid, Torsemide/Torsemide acid and Piretanide are actual dose (mg) multiplied by constant 40, 0.8, 2, or 6.67, respectively.

Doses will be imputed as zero for study days where no use was reported.

IV medications other than loop diuretics

Other IV medications include not limited to Dopamine, Dobutamine, Milrinone, Enoximone, Norepinephrine, Epinephrine, Nesiritide, Levosimendan, Isosorbide Dinitrate, Nitroglycerin, Nitroprusside, Phenylephrine, Caperitide and Other (including but not limited to Danshen).

The number of subjects using each medication will be presented in the same way as IV loop diuretic medications.

The average dose over the time administered of the medication will be presented separately for each medication at each reported time point. No equivalent dose unit among other IV medications will be converted.

Note that the frequency (number and percentage) of subjects using IV loop diuretic and vasoactive agents through Day 5 is an efficacy endpoint and it's discussed in [Section 2.2.3](#).

Other non-IV prior medications & other non-IV medications

The number and percentage of subjects using other non-IV medications will be summarized for each of the time periods for general, ACE inhibitor (ACEi), angiotensin inhibitor (ARB), ACEi or ARB, beta blocker, PO loop diuretics, other PO diuretics, calcium channel blockers, aldosterone antagonist and cardiac glycosides.

The number (%) of subjects who have these medications initiated during their index hospitalization and subjects who have these medications increased during the period following discharge from the index hospitalization will also be presented.

The average daily dose administered will be summarized at each time point for each medication within the loop diuretics, ACEi, ARB, beta blocker, aldosterone antagonist, ARNi and direct renin inhibitor.

Other non-IV medications taken prior to and after the start of study drug will be presented by the ATC and preferred terms.

Other prior and concomitant medications

All other concomitant medications (not included in above classes) and significant non-drug therapies, 30 days prior to screening and ongoing basis until subjects completed or discontinued from the study, will be summarized respectively by ATC therapeutic class, preferred term, and treatment group for the SAF population.

Alternative medicine or herbal medicine will also be presented for the SAF population.

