### **Other efficacy objectives**

- To evaluate the effect of serelaxin as compared to placebo on reducing time to moderate or marked improvements in dyspnea assessed by Likert scale through Day 5
- To evaluate the effect of serelaxin as compared to placebo on changes of dyspnea by VAS-AUC through Day 5
- To evaluate the effect of serelaxin as compared to placebo on reducing the time in index ICU/CCU through Day 5
- To evaluate the effect of serelaxin as compared to placebo on prevention of renal dysfunction or worsening of renal function through Day 5
- To evaluate the effect of serelaxin as compared to placebo on reducing the time to re-hospitalization due to HF and renal failure through Day 180
- To evaluate the effect of serelaxin as compared to placebo on reducing the composite endpoint of CV death or re-hospitalization due to HF/renal failure through Day 180
- To evaluate the effect of serelaxin as compared to placebo on time to in-hospital worsening heart failure through Day 5 where the in-hospital worsening heart failure is defined by symptoms only, signs only, and both symptoms and signs
- To evaluate the effect of serelaxin as compared to placebo on reducing the total intravenous loop diuretic dose, vasoactive and inotropes drug usage through Day 5
- To evaluate the effect of serelaxin as compared to placebo on the changes from baseline in cardio-renal biomarkers on Days 2 and 5

[figure not shown]

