2.2.2 Secondary efficacy variables and analyses

There are three secondary variables:

- WHF through Day 5
- CV death through Day 180
- All-cause death through Day 180

All of these secondary variables are time-to-event variables. The hypothesis will be tested based on the FAS at a significance level of 0.025 (one-sided).

The three secondary variables will be tested using hierarchical testing procedure in controlling overall α of 0.05 (Bretz et al 2009). If primary endpoint is significant, WHF will be tested first at α of 0.05. If WHF is significant at the same α level then will proceed to test CV death and only if CV death is significant then will test all-cause death at α of 0.05.

WHF through Day 5

Time to WHF through Day 5 will be analyzed using Gehan's generalized Wilcoxon test. Subjects died in the 5-day period will be considered as having WHF event. Event date and time will be used at calculating the time to event for better precision, and convert it back to days.

Time-to-event (days) = (first event date/time – baseline date/time),

For those subjects without events, the censoring date will be the earlier of

- Hour 120 (5 days)
- The last date at which the vital status was known, including last visit or contact

Kaplan-Meier curves will be presented graphically by treatment group and Kaplan-Meier estimates for selected time points with 95% confidence intervals will be tabulated.

In addition, analyses will be performed using a modified definition of WHF, e.g. subjects with (1) worsening signs AND symptoms or (2) IV intervention and/or mechanical support. Another sensitivity analyses that exclude subjects whose only symptom is abdominal bloating/discomfort or fatigue/decreased exercise tolerance will also be provided.

CV death through Day 180

CV death will be analyzed with a log-rank test. The time-to-event will be calculated days by subtracting the randomization date from the event date. Number and percentage of subjects who died from cardiovascular reasons based on the number of subjects in the population as denominator will be provided by treatment group. The hazard ratio (relative risk) and its associated two-sided 95% confidence interval will be estimated based on a Cox proportional hazards model with treatment assignment as a factor.

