Descriptive statistics of the area under the curve for the dyspnea VAS change from baseline scores will be presented at each time interval of interest by treatment group. Treatment groups will be compared by presenting the mean difference and corresponding 95% CI and using ANCOVA model with baseline VAS as a covariate.

For those subjects who have at least one post-baseline assessment, their AUC will be approximated by $\sum_{k=2}^m w_k \tilde{y}_k$, where $\tilde{y}_k = 0.5(y_k + y_{k-1})$, $w_k = (t_k - t_{k-1})/(t_m - t_1)$, and y_j is the change-from-baseline in dyspnea VAS value at time t_j , for $j = 1, \dots, m$, in which $t_1 < \dots < t_m$. m is the number of measurements for a subject and t_1 is time of the baseline, that is, $t_1 = 0$ and $y_1 = 0$. The scheduled time will be used in the calculation.

In addition, descriptive statistics for the baseline values, the post-baseline values, and the change from baseline value will be provided at each scheduled time point by treatment group.

Length of stay in index ICU/CCU

The length (days) of stay in ICU/CCU will be obtained from eCRF page directly. If the information is missing in eCRF page or subjects who die during the initial hospitalization, the maximum number of days in the ICU/CCU over all subjects in FAS will be assigned. It will be analyzed using a Wilcoxon rank sum test.

Renal dysfunction or in-hospital worsening of renal function through Day 5

Worsening renal function is defined as an increase in serum creatinine of ≥ 0.3 mg/L (27 $\mu\text{mol/L}$), from the values measured at baseline. A subject who meets the criteria at any time during the 5 days after infusion will be counted once; the chi-squared test will be performed for comparing two treatments.

Number and percentage of subjects will be displayed by treatment and visit for the following category: ≥ 0.3 mg/L increase in serum creatinine.

Additional summaries of serum creatinine and eGFR are discussed in [Section 2.4.2.2](#), Clinical chemistry.

Time to CV death or rehospitalization due to heart failure (HF)/renal failure (RF) through Day 180

Time-to-event (in days) will be calculated using time of first event of adjudicated CV death or adjudicated rehospitalization due to HF/RF minus time of randomization. If the reason for adjudicated death or rehospitalization is unknown, it will be considered as the event. The analysis and censoring method will be performed similarly to time-to-CV death.

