Time to rehospitalization due to heart failure (HF) or renal failure (RF) through Day 180

Time-to-event (in days) will be calculated using time of first event of adjudicated rehospitalization due to HF or RF minus time of randomization. If the reason for adjudicated rehospitalization is unknown, it will be considered as the event.

The analysis and censoring method will be performed similarly to time-to-all-cause-death.

Due to competing risk between death and rehospitalization, the difference in mortality between the treatment groups may mislead the results. In this case, the composite endpoint of Time to CV death or rehospitalization due to heart failure (HF)/renal failure (RF) through Day 180 provides more reliable results.

Time to in-hospital worsening heart failure through Day 5 by symptoms and signs

Time-to-event (in days) will be calculated using time of first event of in-hospital worsening heart failure through Day 5. The worsening heart failure is defined by symptoms only, signs only, and by both symptoms and signs. The analysis and censoring method will be performed similarly to time-to-WHF.

Use of IV loop diuretic and vasoactive agents through Day 5

The subjects with intravenous diuretic and vasoactive therapy (yes/no) during 5 days after study medication infusion will be analyzed using chi-squared test.

The medications of interest are collected in two eCRF pages: “IV loop diuretic medications for heart failure” and “IV medications other than loop diuretics” ([Section 2.1.10](#)). The summaries of doses for those medications are also addressed in [Section 2.1.10](#).

Change from baseline in cardio-renal biomarkers through Day 2 and Day 5

Biomarkers related to cardiac and renal function/injury including but not limited to high sensitivity troponin T, NT-proBNP, and Cystatin C will be collected at baseline, at 48 hours (Day 2) and 120 hours (Day 5) post infusion. This list of potential biomarkers may be changed or expanded further as it is recognized that more relevant or novel biomarkers may be discovered.

Details are described in the separate biomarker statistical analysis plan.

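### The zero-dose rule for IV loop diuretics counts unobserved days after withdrawal as diuretic-free, so the descriptive cumulative dose looks lower in the arm with more early exits

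*SAP*

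**What the plan says.** Protocol 2.2 lists, among the other efficacy objectives, "reducing the total intravenous loop diuretic dose, vasoactive and inotropes drug usage through Day 5". The SAP splits this objective in two.

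- **Use.** Table 2-5 (row 8) and section 2.2.3 analyse yes/no use on the FAS: "The subjects with intravenous diuretic and vasoactive therapy (yes/no) during 5 days after study medication infusion will be analyzed using chi-squared test". Section 2.2.3 then refers the reader to 2.1.10 for doses.
- **Dose.** Section 2.1.10 plans "cumulative use (total dose as the sum from Day 1) at 48 hours" and again at Day 5, in furosemide equivalents. The analysis set follows from "Unless specified, the use of all concomitant medications will be summarized using the SAF population". No test or confidence interval is planned. Medication data are recorded "on a daily basis while hospitalized through Day 5", at discharge and at later visits. The section then states: "Doses will be imputed as zero for study days where no use was reported".

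Two other provisions bear on the rule. Protocol 5.5.10 says that data due after withdrawal of consent are missing. SAP 2.1.3 says that missing values outside the efficacy endpoints are generally left unimputed unless the SAP specifies otherwise.

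**The concern.** A day without reported use can mean three things: the patient was observed and received none, the patient had died, or the patient had left and nobody knows. The rule gives all three the value zero. For the first it is correct, and it is reasonable after discharge alive. For the third it replaces an unknown with the most favourable possible value, against the protocol's own statement that such data are missing. For the second it is factually true, but the resulting low total says nothing about reduced need for diuretic.

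The objective treats a lower dose as better. A patient who leaves early therefore moves the arm's summary in the favourable direction. Because 2.1.10 is the only place where total dose is reported, a reader judging that part of the objective has no other figure to set against it.

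**Working it through.** The documents give no expected diuretic dose and no rate of death or withdrawal within 5 days, so the plan has no figure of its own to reproduce here. The sample size of 1,520 plays no part. Daily dose (40 or 80 mg), exit day and loss rates below are assumptions for illustration, with dosing constant over time.

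**1. One patient.** Recorded share of a constant-rate 5-day total = last observed day / 5.
- Last observed on Day 1, 2, 3 or 4: 1/5 = 20%, 2/5 = 40%, 3/5 = 60%, 4/5 = 80%.
- At 80 mg/day with exit at the end of Day 2: 2 × 80 = 160 mg recorded; the constant-rate 5-day figure is 5 × 80 = 400 mg.
- For a withdrawn patient, 160 mg is only the observed part of an unknown total. For a patient who died, 160 mg is what was given and 400 mg is hypothetical.

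**2. One arm.** Shortfall of the mean against the constant-rate total = share lost × zero-filled days / 5.
- 1% lost, 1 day: 0.01 × 1/5 = 0.2%.
- 5% lost, 4 days: 0.05 × 4/5 = 4.0%.

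**3. Between arms, with identical true daily dosing.** Artificial difference = difference in share lost × zero-filled days / 5. The 5-day mean is 200 mg at 40 mg/day and 400 mg at 80 mg/day.
- 2% v 1%, 3 days: 0.01 × 3/5 = 0.6%, or 1.2 mg and 2.4 mg.
- 3% v 1%, 3 days: 0.02 × 3/5 = 1.2%, or 2.4 mg and 4.8 mg.
- 5% v 2%, 3 days: 0.03 × 3/5 = 1.8%, or 3.6 mg and 7.2 mg.
- Deliberately extreme: every treatment failure in the RELAX-AHF post-hoc analysis (Protocol 6.4.3: 11.9% placebo, 6.4% serelaxin) is lost with 4 zero-filled days: 0.055 × 4/5 = 4.4%, or 8.8 mg and 17.6 mg. Failure includes every death through Day 5, so these rates are a ceiling on early death in that study. Early withdrawal is not bounded by them.

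**4. Dose per day alive and observed.** The patient in step 1 contributes 160/2 = 80 mg/day, the same as a patient followed throughout (400/5 = 80 mg/day). With equal constant dosing the artificial difference is 0.

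If dosing falls over the 5 days, the shifts in steps 2 and 3 shrink, and the per-day figure is higher for early leavers. That is a reason to show the two summaries together.

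**The case against.** The strongest reply is that this is a concomitant-medication table, not an endpoint. It reports what was given, and a patient who has died is given nothing. Early death is already counted in the primary composite, in worsening heart failure and in mortality. A plain sum of doses received would be truncated in the same way without the zero rule. SAP 2.1.3 ends the post-baseline phase at death or last follow-up, so study days might be read to exclude later days. Few patients are affected: those who stop study drug stay in follow-up (Protocol 5.5.9), and nobody can be declared lost before the scheduled end-of-study visit (Protocol 5.5.11).

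Most of this stands and limits the point. It does not cover withdrawal of consent, where the dose is unknown and the protocol calls it missing. Reading study days narrowly leaves the same truncated total unless the patient is dropped from the Day 5 summary, which the SAP does not say.

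Stronger readings are tempting but unsupported:
- **That a tested diuretic result is biased.** The tested analysis is yes/no use on the FAS, and the SAP does not apply the dose rule to it.
- **That 160 mg is 60% too low for a patient who died.** It is the true dose; the 400 mg comparator is hypothetical.
- **That the rule favours serelaxin, or always dilutes a true reduction.** It favours whichever arm loses more patients. A true serelaxin reduction would be diluted only if placebo lost more.
- **That death must be scored as the worst value here too.** The SAP does so for ICU/CCU stay ("subjects who die during the initial hospitalization, the maximum number of days in the ICU/CCU over all subjects in FAS will be assigned") and worsening heart failure ("Subjects died in the 5-day period will be considered as having WHF event"), but those are tested endpoints. A summary of milligrams given need not follow them.

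**Conclusion.** The point holds as a minor defect in a descriptive summary. Zero is the wrong value for days after withdrawal of consent or last contact. After death it is the true dose, but the truncated total needs context before anyone reads it as benefit. The direction is certain: more early exits mean a lower reported total.

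The size is probably small. It is 0.6% of the 5-day mean per percentage point of difference in early loss with three zero-filled days, and 4.4% in the extreme case. Every such figure rests on assumed loss, exit day and constant dosing, because the documents supply none of these for this trial. Type I error, power and the primary, secondary and tested results are untouched.

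**What to change.** Replace the imputation sentence in SAP 2.1.10 before unblinding with a rule to this effect: zero is assigned only to days on which the patient was alive and under observation with no IV loop diuretic recorded, or had been discharged alive; days after withdrawal of consent or last contact are missing; for patients who die, the total is the dose given up to death.

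Beside the cumulative totals, add the furosemide-equivalent dose per day alive and observed, and the number of deaths and withdrawals before 48 hours and before Day 5 by arm.

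Two other repairs are best avoided. A worst rank has no place in a table of mean, SD, median, minimum and maximum milligrams, and multiplying a withdrawn patient's observed daily mean by 5 assumes that early dosing continues unchanged.

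The cost is one revised sentence, a little programming on dates already collected, one extra summary row and the exit counts. A few patients will have an incomplete Day 5 total.
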